F12A. Identification of blood components from LAPS donors: The blood center will receive notification from the coordinating center indicating which of the LAPS donors (donor-ID and BUI) and their donations require recipient record review. For purpose of this study, individuals at the blood center who are retrieving records on the LAPS donors will not be informed of the antibody status of the donors. It is possible that the blood center's other staff may have previously been informed of the antibody test results and that some leukocyte antibody donors have been identified and notified of their antibody status per the blood center's procedures. The blood center will identify all donations made by each donor: index donation + all donations after the index donation + all donations made within two years prior to the index donation. The blood center will identify all the plasma rich components made from these donations and where these components were distributed.

LAPS donor enrollment began in September 2006 and was completed in May 2007. Donations made after the index donation will be available for the study in the REDS-II database. However, plasma products from some of these subsequent donations may not have been transfused due to implementation of TRALI risk reduction programs (which preferentially manufacture transfusable plasma components from donations by male donors) in late 2007 or early 2008.

F12B. Data management of blood components from LAPS donors: The blood center will enter all the donation information and the component distribution data for each donation into a web based system developed and maintained by the Coordinating Center. The information needed will be donation date, blood unit identifier (BUI), type of component, if/where (hospital) each component was distributed to, and the date the component was distributed. Once all the data have been entered into the computer, the blood center staff will identify all blood components (i.e. plasma components, apheresis platelets, and whole blood) that are eligible for study.

F12C. Notification of hospital transfusion service regarding blood components requiring record review: The blood center staff will notify by a letter the medical director of the hospital transfusion service that the recipient record review is needed for the list of blood components. The letter will also ask the transfusion service/blood bank to determine the disposition of each

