HLA antibody positives are those donors whose samples show a normalized background ratio (NBG) of 10.8 or higher in HLA Class I antibody testing and an NBG ratio of 6.9 or higher in HLA class II antibody testing by the Luminex method. These cut-offs represent a mean + 3 standard deviations of a log transformed distribution of values in non-transfused males enrolled in LAPS-I. For purposes of this protocol, LAPS HLA antibody negative donors will be defined as having NBG ratios for both class I and class II antibodies that are less than the mean + 2 standard deviations of the non-transfused LAPS males; this equates to an NBG value of <4.6 for Class I and <3.4 for Class II. A random sample consisting of an equal number of gender and parity frequency-matched antibody negative donors will also be selected for each participating Center.

The Coordinating Center will provide the BUI for each index donation and BUI for each subsequent donation for the study and control donors. Each blood center will then identify all the components made from these donations and their distribution to the hospitals. In addition, the REDS-II Center will identify donations made by the study donor within two years prior to the index donations, components (by component type) made from such donations and the hospitals that received these components. The component distribution data will be entered into the web based screening data forms developed and maintained by the Coordinating Center.

F24B. Other activities at the Coordinating Center: Some blood components made after the index donation may not be subject to recipient record review due to the fact some of the REDS-II participating centers may already be diverting female plasma away from transfusion to the fractionation. The interval prior to the index donation may be extended to get sufficient numbers of components for recipient record review. However, the need to go back further in time for donations is likely to be negligible based on the data on HLA antibody prevalence in LAPS donors and their prior donations.

The coordinating center will review these reports to evaluate the number of plasma rich components that were distributed to the participating hospitals. If the number of components from the antibody positive LAPS donors exceeds the number needed for the study, selection criteria will be developed to choose which components will be subject to record review.

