HLA antibody prevalence in blood donors*	Percent of TRALI that are antibody mediated**	Average # components per transfusion episode***	'control' r	Number required in each of 'case' and 'control' recipients arms for different power estimates		
			80%	85%	90%	
8.5%	80%	6	806	917	1067	
9.0%	80%	6	886	1007	1175	
10.0%	80%	6	1034	1178	1379	

* Results for LAPS show the HLA prevalence to be about 16% for women and about 1% for men, hence overall prevalence of HLA antibodies in units transfused in hospitals participating in LAPS-II is likely to be in the range of 8.5% to 10%.

** Approximately 80% to 85% of TRALI cases are thought to be antibody mediated. The required sample size decreases as the immune mediated percentage increases, thus conservatively 80% is used in the table.

*** Recipients receiving an apheresis component are assumed to receive no other components during the transfusion episode. Recipients receiving an FFP (or other plasmas) component are assumed to receive on average a total of 6 components during the transfusion episode, and as a worst case scenario the additional components are assumed to be high risk TRALI components.

H4. Sample size and power selected for the study: From the above table and the details provided in Appendix D, the sample size selected was 1,175 for the antibody positive components and 1,175 for the antibody negative components. This number will give 90% power to detect a TRALI rate difference between the two groups of recipients. This conservatively assumes that a transfusion episode consists of 6 components although apheresis platelet component transfusion is most often a single unit transfusion episode. The percentage of TRALI that is antibody mediated is assumed to be 80% which may also be a conservative estimate. To the above number, a 10% margin is added to account for missing records etc. Therefore, the total number of antibody positive and antibody negative components is 1,295 for each group.

Based on OSMB recommendations we plan to conduct an interim analysis to see if the estimated sample size is adequate. The interim analysis will assess the average number of components per transfusion episode (assumed to be 6) and the TRALI incidence per component of unknown HLA status (assumed to be 0.18%). If the average is much greater than 6 or the incidence much lower than 0.18%, then increasing the sample size will be considered. A detailed description of the interim analysis is provided in Appendix H.

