There is no risk to the study donors that will arise from this proposed research except that very few donors might be deferred from donating blood in the future if found to be implicated in TRALI; the possibility of such deferral is already included in the original LAPS-I informed consent. Also, donors with HLA antibodies but who are not implicated in TRALI may need to be diverted from apheresis platelet donation based on recent AABB recommendations; however, this outcome would result from donor participation in the original LAPS protocol and is not a consequence of this proposed protocol. Donor consent for proceeding with investigation of the recipients of their donations will be waived because such investigation falls within the expected transfusion medicine practice.

The study recipients of blood transfusion will be selected from participating hospitals and are those patients who have already received the study blood components from antibody positive and negative LAPS study donors. Transfusion recipient consent will be waived because: (a) this study involves record review of previously recorded clinical information and therefore poses minimal risk related to loss of confidential health information (b) all data will be managed in a confidential manner, in particular, the centralized database will not contain patient's name or the hospital's medical record number, (c) the access to recipient data will be restricted to authorized individuals, and (d) the study cannot be performed if the recipient consent is required because of the significant number of recipients who may have already expired after the transfusion due to the known high mortality rates after transfusion from their primary disease.

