For blood donors from the LAPS, some donors without leukocyte antibodies will be excluded due to the fact that the number of antibody negative LAPS donors exceeds the numbers needed for this study.

K. Informed consent

Consent will be waived for blood donors since recipient investigation on blood donations from routine blood donors is a known part of general transfusion medicine practice. Also, there is no risk to the donors except for potential for loss of confidentiality of private health information. Safeguards will be in place to protect the confidentiality of the information. There will be a small risk that a donor who is not part of LAPS may be deferred from donating blood in the future if the donor is clearly implicated in a case of TRALI or is found to have antibodies upon recall testing. However, this risk is no different than if such a donor was found to be implicated or involved in a TRALI case that occurred outside of this study.

Informed consent from transfusion recipients is also waived because all recipient data will be obtained and maintained in a confidential manner and therefore the risk to the recipients is minimal from the loss of confidential private health information. The Centralized data will be maintained at Westat, the coordinating center for REDS-II research program. Westat has considerable experience in managing centralized database to ensure confidentiality of the donor and recipient data. All resulting publications will not contain recipient names or other personal identification information. The data will be linked to permit investigation of additional donors in those TRALI cases which are identified through the research and which were not previously reported to the blood bank. Potential for loss of confidentiality of private health information exists, but several safeguards will be in place to protect the information.

L. Data analysis

The primary analysis will compare the TRALI incidence among case recipients to the TRALI incidence among control recipients. Fisher's exact test for 2x2 tables will be used. The presumed statistical significance will imply HLA antibody in a transfused blood component is a risk factor for TRALI. Then secondary analysis will estimate;

- the probability of a HLA antibody-positive high risk component causing TRALI
- the probability of a HLA antibody-negative component causing TRALI
- the probability of a component of unknown HLA antibody status causing TRALI

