For each HLA positive donor in the study, we consider all of this donor's components in the study period, and enroll recipients of these components as case subjects. In our case recipient group, we will know that one component is HLA positive and that any other components (the number of other components can vary for each recipient) the recipient receives have unknown HLA status. For each HLA negative donor in the study, we consider all of this donor's components in the study period, and enroll recipients of these components as control subjects. In our control group, we will know that one component is HLA negative and that any other components the recipient receives have unknown HLA status. Assume the number of components a recipient receives can be anything from 1 to 11, and averages 6. (Of minor note, the case and control groups will have a higher mean number of components than the overall recipient mean. The reason is that recipients with greater number of components have a higher chance of selection into the study, i.e. since we select components and find the recipient that

received that component, then a recipient with 11 components has 11 chances to be selected, while the recipient with a single component has just 1 chance to be selected).

Using the estimates of TRALI incidence per component (conditional on whether a component is HLA positive, HLA negative, or unknown HLA status), we can estimate the TRALI incidence per case recipient and per control recipient by first calculating the probability of not developing TRALI when receiving on average of 6 components (range 1-11), and then taking the complement of that probability to estimate the probability of the recipient developing TRALI after receiving these components. As an example, a case recipient who receives one HLA antibody-positive high risk component and two high risk components whose HLA status is unknown would have a probability of not developing TRALI equal to $(0.0159) \times (0.0018) \times (0.0018)$ and a probability of developing TRALI equal to $1-\{(0.01.59) \times (0.0018) \times (0.0018)\}$. Using this method, we estimated that the TRALI rates would be about 2.32% for case recipients and 0.79% for control recipients.

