The estimate of 0.79% for control recipients is close to the Finlay estimate (0.85%=7/820) as expected. The Finlay estimate is the TRALI incidence for recipients transfused with components of unknown HLA status. Knowing that one of the transfused components is HLA negative lowers the risk slightly, while the greater average number of components in the control group raises the risk slightly, for a net negligible change in the risk. The estimate of 2.32% in case recipients is less than the composite estimate for other lookback studies (2.7%=5/184). This too is expected, as the other lookback studies only considered components from donors who had been 'implicated' in a TRALI incident.

If the average number of transfused components per recipient were 4 rather than 6, then the TRALI rate estimates in the case recipient group and control recipients groups are lowered to 2.0% per case recipient and 0.5% per control recipient. The statistical power of the study increases as average number of components decreases. Conversely, the statistical power of the study decreases as the average number of components increases. If the interim analysis finds the average to be larger than 6, then increasing the sample size will be considered (see Appendix H). A one-sided 0.05 level test with samples of 1,175 in each of the two recipient groups will have 90% power to statistically detect a greater TRALI incidence among case recipients if 6 components are transfused (statistical power computed using StatXact for an exact conditional test comparing two binomial proportions).

Appendix E: Expected participating hospitals for LAPS-II: IRB, type of medical records, and difficulty in accessing records

No.	No. Participating Hospital Name		Type of IRB (check one)			Patient records (Check one)		On a scale of 1-5 how easy is it to obtain access to medical records?				
							Very easy			Very difficult		
		Hosp	Univ	Other	Electro- nic	Paper	1	2	3	4	5	
		Но	xwort	h Bloo	d Center			1				
1	University Hospital		X		Х		X					
2	Christ Hospital	Х			Х			Х				
3	Jewish Hospital	X			Х			х				
4	Good Samaritan	X			Х			х				
	Hospital											
	The	e Institu	ite for	Transf	fusion Me	edicine						
5	UPMC Presbyterian		Х		Х			Х				
6	UPMC Shadyside		Х		Х			х				
7	Children's Hospital of Pittsburgh of UPMC		X			Х			Х			
8	UPMC Passavant		х			х			Х			
9	UPMC St. Margaret		х		х				Х			
10	Magee-Women's Hospital of UPMC		X		Х				Х			
11	UPMC McKeesport		Х			Х			Х			

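### The crude primary Fisher test leaves component type unbalanced between the arms, although the protocol's own model makes it a strong determinant of background TRALI risk

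*Protocol*

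**What the plan says.** Cases are recipients of an antibody-positive plasma-rich component; controls are recipients of an antibody-negative one (Protocol F1). On choosing control donors, F24A says: "A random sample consisting of an equal number of gender and parity frequency-matched antibody negative donors will also be selected for each participating Center". F10 gives every centre equal component quotas for the two arms. F24B leaves the rule for choosing among surplus components to be developed, and allows the donation window to be extended backwards.

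Section L says: "The primary analysis will compare the TRALI incidence among case recipients to the TRALI incidence among control recipients". It names Fisher's exact test for 2x2 tables and reads significance as implying that HLA antibody is a risk factor. The covariate analyses that follow in Section L are exploratory and do not adjust this comparison.

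The footnote to Table-12 says: "Recipients receiving an apheresis component are assumed to receive no other components during the transfusion episode". Plasma recipients are taken to receive six components on average, the others all treated as high-risk. H3 puts the overall mix at 70% plasma and 30% apheresis platelets. No section gives the mix by arm.

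**The concern.** The planning model makes component type a main driver of background risk, because plasma recipients receive several other units and apheresis recipients none. Donor-level matching on gender and parity does not fix what the donors' components are. If the plasma share differs between arms, the crude comparison mixes the effect of the study unit with that of the accompanying units.

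The protocol names one route to a systematic difference. H6 says that "donors with HLA antibodies but who are not implicated in TRALI may need to be diverted from apheresis platelet donation". Platelet components would then be lost from the case arm only, its plasma share would rise, and the bias would favour a positive result. F12A adds that some donors may already have been told their antibody status.

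The mix itself is not firmly known. F8 counts 694 plateletpheresis and 705 plasma components from 75 donors, about 50/50, while H3 cites 30/70 from a 75-donor pilot. About 140 donors per arm supply some 18.5 components each (F8), so a few frequent apheresis donors can shift an arm's mix.

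**Working it through.** **Planned figure.** Appendix D states that "A one-sided 0.05 level test with samples of 1,175 in each of the two recipient groups will have 90% power", with the expectation that "the TRALI rates would be about 2.32% for case recipients and 0.79% for control recipients", and gives the method as "statistical power computed using StatXact for an exact conditional test comparing two binomial proportions". Exact enumeration of the one-sided Fisher test at 2.32% against 0.79% gives 90.0% at 1,175 per arm, 85.0% at 1,007 and 80.0% at 886. This matches the 9.0% row of Table-12.

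**Risk model.** Inputs from H3, Table-12 and Appendix D: per-component risk of 1.59% (antibody-positive), 0.04% (antibody-negative) and 0.18% (unknown status). A recipient whose study unit has risk p and who receives m further unknown units has risk

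1 − (1 − p)(1 − 0.0018)^m.

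For apheresis m = 0. For plasma m = 5 if the six units include the study unit. m = 6 allows for Appendix D's remark that selecting by component favours recipients of more units. With m = 6 and a 70/30 mix:

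- case: 0.7 × 2.65% + 0.3 × 1.59% = 2.33%
- control: 0.7 × 1.11% + 0.3 × 0.04% = 0.79%

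These are essentially the planned rates. With m = 5 they are 2.21% and 0.67%.

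**Background gap with no HLA effect** (every unit at 0.18%). Plasma: 1 − 0.9982^6 = 1.08% (m = 5) or 1 − 0.9982^7 = 1.25% (m = 6). Apheresis: 0.18%. The ratio is 6.0 or 7.0.

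**False-positive rate of the crude test.** Arm risk = f × plasma risk + (1 − f) × 0.18%, where f is the arm's plasma share; 1,175 per arm, one-sided 0.05. All arm-specific shares are assumptions.

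| Plasma share, case/control | Arm risks, m = 5 | False positive | Arm risks, m = 6 | False positive |
|---|---|---|---|---|
| 70/70 | 0.81% / 0.81% | 3.2% | 0.93% / 0.93% | 3.2% |
| 70/60 | 0.81% / 0.72% | 5.3% | 0.93% / 0.82% | 5.7% |
| 70/50 | 0.81% / 0.63% | 8.6% | 0.93% / 0.72% | 9.9% |
| 70/40 | 0.81% / 0.54% | 13.8% | 0.93% / 0.61% | 16.4% |
| 60/70 | 0.72% / 0.81% | 1.7% | 0.82% / 0.93% | 1.7% |
| 50/70 | 0.63% / 0.81% | 0.9% | 0.72% / 0.93% | 0.8% |

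The unrounded unit risk, (7/6,888)/(0.51/6 + 0.49) = 0.177%, changes these by at most about 0.3 points.

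**Power with the planned effect.** At 50/70 and m = 6 the case rate is 0.5 × 2.65% + 0.5 × 1.59% = 2.12% against 0.79%, and power falls from 90% to 83%. With m = 5 it falls from 92.5% to 87.3%.

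**Chance imbalance.** Averaging over a random case-minus-control difference in plasma share with assumed SD of 5, 10 or 15 points (m = 6) gives false-positive rates of 3.3%, 3.7% and 4.3%.

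**Stratified test.** One-sided Mantel-Haenszel test by component type, m = 5, 200,000 simulations. With no HLA effect and shares of 70/70, 75/65, 80/60 and 90/50, rejection is 4.7–5.1% without continuity correction and 2.5–3.2% with it. Crude Fisher gives 3.2%, 5.3%, 8.4% and 18.6%. With the planned effect, power with the correction is 92.7% at 70/70, 91.0% at 60/80 and 83.8% at 50/90; crude Fisher gives 92.5%, 85.0% and 74.0%.

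**The case against.** The strongest reply is that no imbalance is documented. Every case/control split above is assumed. Controls are a random sample, matched on gender and parity within centre, and centre is already balanced by equal quotas. Chance swings go both ways, and averaged over both directions the error stays below 5%; a 10-point gap barely exceeds it. All of this stands.

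The diversion route is also limited by the protocol's dates. Index donations ran from September 2006 to May 2007 (F12A), and F26 describes a window of about two years back and one forward, ending around May 2008. The recommended deadline for apheresis platelets was November 2008 (Section E). This weakens the route without closing it, because F12A takes in all donations after the index donation.

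A reader might infer that case components come from an earlier and control components from a later, safer period, since "plasma products from some of these subsequent donations may not have been transfused due to implementation of TRALI risk reduction programs". The documents do not support that as a finding. Those programmes act by donor sex, which is matched, so they affect both arms. Differing donation periods remain a possibility, because the window may be extended with no rule keeping it equal between arms, but the size of any effect cannot be computed from the protocol.

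A separate analysis plan might add adjusted analyses. Even so, the protocol itself names the crude test as primary and attaches the causal reading to it.

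**Conclusion.** The point holds as a recommended improvement; the primary analysis has not been shown to be wrong. By the protocol's own assumptions, plasma recipients carry six to seven times the background risk of apheresis recipients, and neither the matching nor the primary test accounts for it. Error exceeds the nominal level materially only if the imbalance is systematic and larger than about 10 points: roughly 9–10% at 20 points and 14–16% at 30. Smaller imbalances bias the estimate or cost power.

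The stronger reading, that a positive result could be wholly an artefact of component mix, is not supported. The planned ratio is 2.32/0.79, about 2.9. With no HLA effect, a 70/50 split gives about 1.3, and even 100/50 gives only 1.71 (m = 5).

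The sizes rest on the assumed shares and on the protocol's model of one component per apheresis episode, about six per plasma episode and 0.18% per unknown unit.

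**What to change.** Make the primary test an exact or Mantel-Haenszel test stratified by component type (plasma versus apheresis platelets). Centre may be added as a stratum. Keep the crude Fisher test as a sensitivity analysis.

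When the component selection criteria foreseen in F24B are written, frequency-match control components to case components on component type. Apply the same donation window to both arms, including any backward extension.

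Component type and donation date are already recorded (F12B), so no new data are needed. The cost is slightly less freedom in choosing control components and a little more analysis work. In the check above, stratifying lost no power when the arms were balanced.
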